### **Expected Outcomes:**

The use of HFNC is expected to achieve an extubation success rate that is comparable to NIV, while offering a lower risk of complications and enhanced patient comfort. The findings of this study are anticipated to provide significant evidence regarding the differences between these two modalities in preventing extubation failure.

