**Secondary Objectives:**

1. To compare CICU length of stay between patients receiving HFNC and those receiving NIV.
2. To compare sedation usage (duration and total dose) between patients receiving HFNC and those receiving NIV
3. To compare COMFORT scale between patients receiving HFNC and those receiving NIV

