	T-piece	Ventilator weaning method using a T-Piece without pressure support.	Categorical	Medical Records on the Method Used	
ABG 1 hour after NIV/HFNC	pH	Arterial blood pH measured 1 hour after initiation of NIV or HFNC.	Numeric	Arterial Blood Gas (ABG) Measurement	
	PCO2	Partial pressure of carbon dioxide (PaCO2) in blood, measured 1 hour after initiation of NIV or HFNC	Numeric	Arterial Blood Gas (ABG) Measurement	
	PaO2	Partial pressure of oxygen (PaO2) in blood, measured 1 hour after initiation of NIV or HFNC	Numeric	Arterial Blood Gas (ABG) Measurement	
	BE (Base Excess)	Base excess or deficit in blood, measured 1 hour after initiation of NIV or HFNC	Numeric	Arterial Blood Gas (ABG) Measurement	
	HCO3	Bicarbonate concentration in blood, measured 1 hour after initiation of NIV or HFNC	Numeric	Arterial Blood Gas (ABG) Measurement	
	PF ratio	Ratio of PaO2 to FiO2, measured 1 hour after initiation of NIV or HFNC	Numeric	Arterial Blood Gas (ABG) Measurement	
	OI/OSI	Oxygenation Index (OI) or Oxygen Saturation Index (OSI), measured 1 hour after initiation of NIV or HFNC	Numeric	Arterial Blood Gas (ABG) Measurement	
Successful Extubation	No Reintubation in 72 hours	Patient does not require reintubation within 72 hours after extubation	Categorical	Based on Clinical Observation	
Extubation Failure	Reintubation within 72 hours	Patient requires reintubation within 72 hours after extubation	Categorical	Based on Clinical Observation	
Reintubation	Reintubasi at 72 hours, 7 days and 28 Days	Frequency of patients requiring reintubation at 72 hours, 7 days and 28 days	Categorical	Based on Clinical Observation	
Mortality in CICU	Mortality During CICU Stay	Number of patient deaths during CICU hospitalization	Categorical	Based on Mortality Records	
Length of CICU Stay	Total Length of CICU Stay (in Days)	Total length of CICU stay measured in days	Numeric	Based on Hospital Records	
Length of Hospital Stay	Total Length of Hospital Stay (in Days)	Total length of hospital stay measured in days	Numeric	Based on Hospital Records	
Sedation usage	Duration of sedation (in Hours) and total dosage	Total duration of sedation after extubation measured in hours and total dosage	Numeric	Based on Hospital Records	
COMFORT scale	Patient's comfort during sedation post extubation	Patient's comfort measured in COMFORT behavioral scale	Categoric	COMFORT behavioural scale assessment	

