### 4.3. Population and Sample

The study population consists of **pediatric patients undergoing post-cardiac surgery** and receiving care in the **CICU at RSUPN Cipto Mangunkusumo, Jakarta**. The study sample will be selected based on predefined **inclusion and exclusion criteria**, with the total sample size determined using an appropriate statistical estimation formula. The sample size estimation will be calculated using the following formula:

$$n1 = n2 = \left( \frac{Z\alpha\sqrt{2PQ} + Z\beta\sqrt{P1Q1 + P2Q2}}{P1 - P2} \right)^2$$

Description:

n1 = n2 = Sample size

Za = Standard deviation for Type I error = 5% = 1,96

Zb = Standard deviation for Type II error = 20% = 0,84

P1 – P2 = Minimum significant difference in proportion = 0,25

P2 = Extubation failure rate with HFNC based on literature is 17% or equivalent to 0,17.

Q2 = 1 – 0,17 = 0,83

P1 = P2 + 0,25 = 0,17 + 0,25 = 0,42

Q1 = 1 – P1 = 1 – 0,42 = 0,58

P = (P1 + P2)/2 = (0,42 + 0,17)/2 = 0,295

Q = 1 – P = 1 – 0,295 = 0,705

$$n1 = n2 = \left( \frac{1,96\sqrt{2x0,295x0,705} + 0,84\sqrt{0,42x0,58 + 0,17x0,83}}{0,42 - 0,17} \right)^2 = 51$$

Meanwhile, when estimating the sample size based on the outcome of reintubation rate reduction, the calculation is as follows

$$n1 = n2 = \left( \frac{Z\alpha\sqrt{2PQ} + Z\beta\sqrt{P1Q1 + P2Q2}}{P1 - P2} \right)^2$$

Description:

P1 (HFNC) = 0.37 (HFNC reintubation rate)

P2 (NIV) = 0.15 (NIV reintubation rate)

P1 - P2 = 0.25 (Difference to be detected)

Q1 = 1 - P1 = 1 - 0.37 = 0.63

Q2 = 1 - P2 = 1 - 0.15 = 0.88

P = (P1 + P2) / 2 = (0.37 + 0.17) / 2 = 0.245

Q = 1 - P = 1 - 0.245 = 0.755

$$n1 = n2 = \left( \frac{1,96\sqrt{2x0,245x0,755} + 0,84\sqrt{(0,37x0,63) + (0,12x0,88)}}{0,25} \right)^2$$

= 45.22 ~ 46 subjects

Similarly, when estimating the sample size based on the outcome of mortality reduction, the calculation is as follows:

$$n1 = n2 = \left( \frac{Z\alpha\sqrt{2PQ} + Z\beta\sqrt{P1Q1 + P2Q2}}{P1 - P2} \right)^2$$

Description:

P1 (HFNC) = 0.1 (Mortality rate with HFNC)

P2 (NIV) = 0.35 (Mortality rate with NIV)

P1 - P2 = 0.25 (The difference to be detected)

Q1 = 1 - P1 = 1 - 0.1 = 0.9

$$Q2 = 1 - P2 = 1 - 0,35 = 0,65$$

$$P = (P1 + P2) / 2 = (0,1 + 0,33) / 2 = 0,225$$

$$Q = 1 - P = 1 - 0,225 = 0,77$$

$$n1 = n2 = \left( \frac{1,96\sqrt{2 \times 0,225 \times 0,775} + 0,84\sqrt{(0,1 \times 0,9) + (0,35 \times 0,65)}}{0,25} \right)^2$$
$$= 42,54 \sim 43 \text{ subjek}$$

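### Table 1 ties the COMFORT score to sedation after extubation, so who is scored, and for how long, depends on another randomised outcome

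*Protocol*

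**What the plan says.** The protocol's readable text describes the COMFORT outcome in one place, its row in Table 1 (Chapter III). One cell reads "Patient's comfort during sedation post extubation" and the next reads "Patient's comfort measured in COMFORT behavioral scale". The row gives no assessment times and no rule for a child who receives no sedative.

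The third item under Secondary Objectives (section 1.5) is "To compare COMFORT scale between patients receiving HFNC and those receiving NIV". It is not limited to sedated children, and neither is the opening statement of research objectives. The second item is "To compare sedation usage (duration and total dose) between patients receiving HFNC and those receiving NIV", which Table 1 specifies as "Total duration of sedation after extubation measured in hours and total dosage". Under Expected Outcomes, HFNC is anticipated to match NIV while "offering a lower risk of complications and enhanced patient comfort".

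**The concern.** The objective is about all children in each arm. The table row places the measurement inside a period of sedation that occurs while the allotted device is in use. If bedside staff follow the row as written:

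- a child who is calm and receives no sedative after extubation has no defined score;
- a child who is sedated briefly contributes only that period;
- a sedated child is scored while the drug may be acting.

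Whether and how long a child is sedated is an outcome that the protocol itself compares between arms. Chapter II gives a reason why it could differ: NIV interfaces are described as uncomfortable for small children, and HFNC as easier to tolerate. Scored children would then be a subset formed after treatment began, and randomisation would no longer protect the comparison. A later analysis plan could not repair this, because scores that were never taken cannot be recovered.

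**Working it through.** **1. Passages side by side.** The objective covers all HFNC and all NIV patients. The Table 1 row covers the period of sedation after extubation. The sedation row just above it is a between-arm outcome in its own right. By contrast, Table 1 times the post-treatment blood gases at one hour from the start of either device, a clock that is the same in both arms. The COMFORT row has no such clock.

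**2. Plan figures available.** The protocol gives no figure for COMFORT and no sedation rate. The only usable input is the group size in section 4.3. Its formula reproduces: ((1.96√(2×0.295×0.705) + 0.84√(0.42×0.58 + 0.17×0.83))/0.25)² = 50.98, so 51 per group. Then 102 × 1.1 = 112.2, rounded up to 113, which the protocol carries as 57 per group. This is needed only to count scored children.

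**3. Selection bias with no true difference (assumed model).** Let discomfort D be N(0,1) in both arms. A child is sedated when a latent trigger with correlation ρ to D exceeds a cut that gives sedated share p. Then

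E[D | sedated] = ρ·φ(z)/p, with z = Φ⁻¹(1 − p).

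- p = 0.6: z = −0.253, φ = 0.386, φ/p = 0.644
- p = 0.4: z = 0.253, φ = 0.386, φ/p = 0.966
- Difference, HFNC (40%) minus NIV (60%): 0.322ρ

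For shares of 70% and 30%, the same formula gives 1.159 − 0.497 = 0.662, so 0.662ρ.

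| Sedated, NIV vs HFNC | Scored, NIV vs HFNC (57 × p) | ρ = 0.3 | ρ = 0.5 | ρ = 0.7 | ρ = 0.9 |
|---|---|---|---|---|---|
| 60% vs 40% | 34 vs 23 | 0.10 | 0.16 | 0.23 | 0.29 |
| 70% vs 30% | 40 vs 17 | 0.20 | 0.33 | 0.46 | 0.60 |
| Equal shares, or all sedated | equal | 0 | 0 | 0 | 0 |

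Entries are in SD; a positive value makes HFNC look worse. Simulation with 2,000,000 children per arm agrees within 0.002 for ρ of 0.3, 0.5 and 0.7.

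**4. A true HFNC benefit of 0.5 SD, same trigger in both arms.** Let the trigger be discomfort plus noise of SD 0.5, so ρ = 1/√1.25 = 0.89 and the trigger SD is 1.118. With 60% of NIV children sedated, the cut is −0.253 × 1.118 = −0.283. In the HFNC arm it lies (−0.283 + 0.5)/1.118 = 0.194 SD above the mean, so about 42% are sedated. Mean discomfort among the sedated is 0.576 (NIV) and 0.328 (HFNC), a difference of 0.25 instead of 0.50. With 40% or 80% of NIV children sedated, simulation gives 0.21 or 0.31. The benefit shrinks but keeps its direction. A ρ of 0.89 is near the top of the range above, and a weaker correlation would shrink it less.

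**5. After the fix.** If all 57 per arm are scored at common times, selection by sedation is removed and the bias in step 3 is zero.

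**The case against.** The strongest reply is that this is a loosely worded table cell and not an analysis rule. The adjacent cell names the scale with no sedation condition, the objectives are unrestricted, and the column headers of Table 1 do not line up well with its cells. The group procedures and flowchart in section 4.9 are figures that could not be read here, and an analysis plan may exist; either could set a COMFORT schedule. Sedation after extubation may also be continued from the ventilated period and not started because of the device. Finally, COMFORT is a secondary outcome with no power calculation.

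Much of this stands. A reader might infer that the protocol limits the comfort analysis to sedated children. It does not say so: no text states that unsedated children go unscored or that scoring stops with sedation. The restriction follows only from taking the row literally. The protocol also does not say that sedatives are given for device discomfort, so the model in steps 3 and 4 is an assumption. Rejection rates and power are not quoted, because they would need a test on a continuous score, and Table 1 types COMFORT as categorical.

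What does not fall away is the mismatch itself. This row is the only readable description of when COMFORT is taken, and it differs from the objective it serves. Sedation continued from before extubation still has a duration that the device could change.

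**Conclusion.** The point holds as an inconsistency between Table 1 and the third secondary objective. Followed as written, the row makes COMFORT scoring depend on sedation use, a separate randomised outcome, and so opens the comparison to selection bias.

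The size cannot be derived from the protocol. Under the assumed model with no true difference, sedated shares of 60% (NIV) and 40% (HFNC) give about 0.1 to 0.3 SD against HFNC for correlations of 0.3 to 0.9. Equal shares or near-universal sedation give about zero, though the scoring window would still track sedation duration.

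A reader might go further and infer that the trial cannot answer the comfort question at all. The protocol does not support that: the bias may be negligible if sedation is similar or near-universal in both arms, and in the true-benefit illustration the effect is diluted without changing sign. The primary outcome is not touched.

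**What to change.** Reword the COMFORT row of Table 1 to match the objective, for example: comfort after extubation on the COMFORT behavioural scale, scored in every randomised child at the same fixed times from the start of HFNC or NIV, whether or not a sedative is being given. State that the arms are compared in all randomised children. Check that the section 4.9 figures agree.

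Record sedation status at each score as a descriptor, not as a condition for scoring or analysis, and report sedation use beside the COMFORT result. This is needed because scoring everyone removes the selection but not the drug's effect on the score: similar scores reached with different sedation use do not mean the same thing.

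The cost is one table row, a field on the case report form, and a few extra bedside scores by the team that section 4.7 already assigns to monitoring. No extra patients are needed, and no change to sedation practice is implied. The change has to be made before scoring begins.

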## CHAPTER IV Research Methodology

### 4.1. 4.1. Study Design

This study employs a Randomized Controlled Trial (RCT) design to compare two intervention groups: patients receiving oxygen therapy using Non-Invasive Ventilation (NIV) and those receiving therapy with High Flow Nasal Cannula (HFNC) using AirvoTM3 Nasal High Flow/HFNC System. Patients will be monitored for the incidence of extubation failure and other clinical parameters throughout their hospitalization.

### 4.2. Study Setting and Duration

This study will be conducted in the Cardiac Intensive Care Unit (CICU) at [name] National General Hospital (RSUPN Cipto Mangunkusumo), Jakarta. The study period will run from January 2025 to December 2025.

### 4.3. Population and Sample

The study population consists of **pediatric patients undergoing post-cardiac surgery** and receiving care in the **CICU at RSUPN Cipto Mangunkusumo, Jakarta**. The study sample will be selected based on predefined **inclusion and exclusion criteria**, with the total sample size determined using an appropriate statistical estimation formula. The sample size estimation will be calculated using the following formula:

$$n1 = n2 = \left( \frac{Z\alpha\sqrt{2PQ} + Z\beta\sqrt{P1Q1 + P2Q2}}{P1 - P2} \right)^2$$

Description:

n1 = n2 = Sample size

Za = Standard deviation for Type I error = 5% = 1,96

Zb = Standard deviation for Type II error = 20% = 0,84

P1 – P2 = Minimum significant difference in proportion = 0,25

P2 = Extubation failure rate with HFNC based on literature is 17% or equivalent to 0,17.

Q2 = 1 – 0,17 = 0,83

P1 = P2 + 0,25 = 0,17 + 0,25 = 0,42

Q1 = 1 – P1 = 1 – 0,42 = 0,58

P = (P1 + P2)/2 = (0,42 + 0,17)/2 = 0,295

Q = 1 – P = 1 – 0,295 = 0,705

$$n1 = n2 = \left( \frac{1,96\sqrt{2x0,295x0,705} + 0,84\sqrt{0,42x0,58 + 0,17x0,83}}{0,42 - 0,17} \right)^2 = 51$$

Meanwhile, when estimating the sample size based on the outcome of reintubation rate reduction, the calculation is as follows

$$n1 = n2 = \left( \frac{Z\alpha\sqrt{2PQ} + Z\beta\sqrt{P1Q1 + P2Q2}}{P1 - P2} \right)^2$$

Description:

P1 (HFNC) = 0.37 (HFNC reintubation rate)

P2 (NIV) = 0.15 (NIV reintubation rate)

P1 - P2 = 0.25 (Difference to be detected)

Q1 = 1 - P1 = 1 - 0.37 = 0.63

Q2 = 1 - P2 = 1 - 0.15 = 0.88

P = (P1 + P2) / 2 = (0.37 + 0.17) / 2 = 0.245

Q = 1 - P = 1 - 0.245 = 0.755

$$n1 = n2 = \left( \frac{1,96\sqrt{2x0,245x0,755} + 0,84\sqrt{(0,37x0,63) + (0,12x0,88)}}{0,25} \right)^2$$

= 45.22 ~ 46 subjects

Similarly, when estimating the sample size based on the outcome of mortality reduction, the calculation is as follows:

$$n1 = n2 = \left( \frac{Z\alpha\sqrt{2PQ} + Z\beta\sqrt{P1Q1 + P2Q2}}{P1 - P2} \right)^2$$

Description:

P1 (HFNC) = 0.1 (Mortality rate with HFNC)

P2 (NIV) = 0.35 (Mortality rate with NIV)

P1 - P2 = 0.25 (The difference to be detected)

Q1 = 1 - P1 = 1 - 0.1 = 0.9

$$Q2 = 1 - P2 = 1 - 0,35 = 0,65$$

$$P = (P1 + P2) / 2 = (0,1 + 0,33) / 2 = 0,225$$

$$Q = 1 - P = 1 - 0,225 = 0,77$$

$$n1 = n2 = \left( \frac{1,96\sqrt{2 \times 0,225 \times 0,775} + 0,84\sqrt{(0,1 \times 0,9) + (0,35 \times 0,65)}}{0,25} \right)^2$$
$$= 42,54 \sim 43 \text{ subjek}$$

Based on these calculations, the required **sample size is 51 subjects per group**, resulting in a total of **102 subjects** for both groups. Considering an **additional 10% to account for loss to follow-up**, the adjusted sample size is calculated as follows:

Additional subjects:

$$10\% \times 102 = 10,2$$

Total subjects after addition:

$$102 + 10,2 = 112,2 \sim 113 \text{ subjek}$$

57 subjects/group

Thus, this study requires **57 subjects per group**, with a total of **114 subjects**.

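### The reintubation sample-size calculation in Protocol 4.3 uses three different NIV rates, its 46 per group fits only an undeclared one, and it makes HFNC the worse arm, against the rest of the protocol

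*Protocol*

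**What the plan says.** Protocol section 4.3 sizes the trial three times with one two-proportion formula (Z values 1.96 and 0.84).

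- **Calculation 1, extubation failure.** HFNC is 0.17. The other rate is 0.17 + 0.25 = 0.42, with no arm named. Result: 51 per group.
- **Calculation 2, reintubation.** It is introduced as "estimating the sample size based on the outcome of reintubation rate reduction". Its inputs are "P1 (HFNC) = 0.37 (HFNC reintubation rate", "P2 (NIV) = 0.15 (NIV reintubation rate" and "P1 - P2 = 0.25 (Difference to be detected". Then follow "Q2 = 1 - P2 = 1 - 0.15 = 0.88" and "P = (P1 + P2) / 2 = (0.37 + 0.17) / 2 = 0.245". The worked formula contains "0,37x0,63) + (0,12x0,88", and the result is "45.22 ~ 46 subjects". No time point is given.
- **Calculation 3, mortality.** HFNC 0.1, NIV 0.35. Result: 43 per group.

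The end of 4.3 rests the sample size on these calculations jointly, takes 51 per group, adds 10% for loss to follow-up and reaches 57 per group, 114 in total. Section 4.5 repeats only the 17% for HFNC and the 25-point difference.

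Two other places bear on direction. Table 1 defines extubation failure as reintubation within 72 hours, and lists reintubation at 72 hours, 7 days and 28 days. The Outcome of Study section expects reintubation to be lower with HFNC than with NIV.

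**The concern.** A sample-size calculation should have one rate per arm, and each line should follow from the one before. Calculation 2 carries three NIV rates, so a reader cannot tell which comparison its 46 per group stands for.

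The arms are a separate problem. Under calculation 2 children on HFNC are reintubated more often than children on NIV. Calculation 1 gives HFNC the lower rate for extubation failure, which by the protocol's own definition is reintubation within 72 hours. If calculation 2 is also meant at 72 hours, one protocol assumes HFNC rates of both 0.17 and 0.37 for the same event. If it is meant at 7 or 28 days, a higher HFNC rate could be explained, but HFNC being worse than NIV could not, because the expected reduction is stated for the later time points as well.

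At stake is whether calculation 2 can be cited as support for the sample size, and whether the declared rates would call for more than the 51 adopted.

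**Working it through.** **Inputs.** All come from Protocol 4.3: Z values 1.96 and 0.84, and the rates listed above. The formula is the protocol's own, with P the mean of P1 and P2, Q = 1 − P, Q1 = 1 − P1 and Q2 = 1 − P2:

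n = [(1.96·√(2PQ) + 0.84·√(P1Q1 + P2Q2)) / (P1 − P2)]²

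**Step 1. Reproduce the printed figures.**

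- Calculation 1 (0.42, 0.17): P = 0.295; (1.2641 + 0.5210)/0.25, squared = 50.98, so 51. It agrees.
- Calculation 2 as worked (0.37, 0.12): P = 0.245; (1.1921 + 0.4889)/0.25, squared = 45.21, so 46. It agrees with the printed 45.22 apart from rounding.
- Calculation 3 (0.10, 0.35): P = 0.225; (1.1575 + 0.4733)/0.25, squared = 42.55, so 43. It agrees. The 0,33 in its mean line should be 0,35, because (0.10 + 0.33)/2 is 0.215, and its Q of 0,77 should be 0,775. Both are clerical, since the worked formula uses the right values.

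**Step 2. Check the lines of calculation 2 as printed.**

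| Line | Printed | Correct for the numbers on the page | With NIV = 0.12 |
|---|---|---|---|
| P1 − P2 | 0.25 | 0.37 − 0.15 = 0.22 | 0.25 |
| Q2 | 0.88 | 1 − 0.15 = 0.85 | 0.88 |
| Mean P | 0.245 | (0.37 + 0.17)/2 = 0.27 | 0.245 |

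Every printed result fits 0.12. The value 0.15 is written twice (P2 line and Q2 line) and 0.17 once; 0.12 appears only inside the worked formula.

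**Step 3. What the declared 0.15 would need.** The protocol does not settle whether the HFNC rate or the difference is to be held, so both are shown.

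- HFNC held at 0.37: P = 0.26, difference 0.22; (1.2158 + 0.5044)/0.22, squared = 61.14, so 62.
- Difference held at 0.25, giving 0.40 vs 0.15: P = 0.275; (1.2377 + 0.5092)/0.25, squared = 48.83, so 49.

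The 0.17 is not developed into a scenario. It occurs once, in a line whose own result contradicts it, and it equals P2 of calculation 1.

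**Step 4. Power of the two-sided 5% pooled z-test**, Φ[(|P1 − P2|·√n − 1.96·√(2PQ)) / √(P1Q1 + P2Q2)]:

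| Pair | n = 46 | n = 51 | n = 57 |
|---|---|---|---|
| 0.42 vs 0.17 | 75.7% | 80.0% | 84.3% |
| 0.37 vs 0.12 | 80.6% | 84.6% | 88.4% |
| 0.37 vs 0.15 | 67.7% | 72.3% | 77.1% |
| 0.40 vs 0.15 | 77.5% | 81.7% | 85.8% |

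**Step 5. Direction.** HFNC at 0.37 exceeds 0.12, 0.15 and 0.17 alike, so no choice among the three NIV rates removes the conflict. In calculation 1 HFNC is at 0.17 and the other arm, NIV by elimination in a two-arm trial, at 0.42. In calculation 3 HFNC is again the better arm. The formula is symmetric, so swapping the labels in calculation 2 leaves n unchanged.

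**The case against.** The strongest reply is that nothing about the trial's size turns on this. The planned number is the largest of 51, 46 and 43; the 51 comes from calculation 1, which reproduces, and 4.5 repeats only that calculation's inputs. With 0.12 as the evident intent, what remains is a transcription slip and swapped labels in a calculation that does not govern. This stands as to size. It does not remove the fault: the inputs as declared do not give the printed result, the section cites that result as support, and putting 0.12 throughout would still leave HFNC as the worse arm.

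Four stronger readings are tempting, and the protocol does not support them.

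- **That the trial is too small, because 62 exceeds both 51 and 57.** This requires holding 0.37 against 0.15 and giving up the 0.25 difference, which is stated in all three calculations. Keeping the difference gives 49, which 51 covers.
- **That calculation 2 contradicts its own introduction.** The introduction speaks of a reduction without naming an arm. The direction comes from Outcome of Study and from calculation 1. Elsewhere (Expected Outcomes, 1.2, 1.3) HFNC is expected only to be comparable to NIV or as effective.
- **That a reader cannot know which effect the trial is powered for.** Section 4.3 gives 0.17 for HFNC, and the 0.42 is NIV by elimination. Only the sentence in 4.5 lacks the comparator and direction.
- **That calculation 2 merely duplicates calculation 1.** That is so only at 72 hours, and no time point is stated.

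**Conclusion.** The point holds and should be fixed. Calculation 2 has three false lines, and its 46 per group is valid only for a pair of rates that the input list never declares. For the declared NIV rate of 0.15 the printed 46 is wrong on either reading: 62 with HFNC held at 0.37, 49 with the difference held at 0.25. Its arm labels conflict with calculation 1 and with the reduction expected under HFNC.

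The planned 51 evaluable and 57 enrolled per group rest on calculation 1 and are not disturbed. Only if the sponsor confirms 0.37 vs 0.15 as the intended reintubation comparison does the power fall below 80% for it, to about 72% at 51 and 77% at 57. These figures assume the protocol's formula, a two-sided 5% test and equal allocation. That 0.12 was intended is an inference from the printed results, and that 0.42 is the NIV rate is an inference by elimination; the sponsor must confirm both.

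**What to change.** In Protocol 4.3, either remove the reintubation calculation as support for the sample size, or reconcile it to one NIV rate with matching difference, Q2, mean and n, a named time point, and arm labels that agree with calculation 1 and Outcome of Study.

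In 4.3 and 4.5, label the 0.42 as the NIV rate, subject to the sponsor's confirmation, and say that the sample size rests on calculation 1. Suggested wording: *The sample size is based on extubation failure within 72 hours. With 51 evaluable patients per group, a two-sided 5% test has 80% power to detect a difference between 42% with NIV and 17% with HFNC.* The sentence should not claim that this is the only pair so powered, since 51 per group gives 84.6% for 0.37 vs 0.12.

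If the sponsor confirms 0.37 vs 0.15, restate the power for that comparison as about 72% at 51 and 77% at 57 per group, with no patients added. In the mortality calculation, correct 0,33 to 0,35 and Q from 0,77 to 0,775; its 43 stands.

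The cost is a text correction in two sections. The downside is a narrower power statement.
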